3.2. Warm Autoimmune Hemolytic Anemia

Autoimmune hemolytic anemia (AIHA) is caused by increased red blood cell (RBC) destruction triggered by autoantibodies that react against RBC antigens with or without complement. Antibodies in warm autoimmune hemolytic anemia (WAIHA) react optimally at 37 degrees Celsius and is the most common type of AIHA, comprising approximately 70-80% of all adult cases [Sokol, 1981]. The most common antibody isotype involved in WAIHA is IgG, with a greater prevalence of IgG1 and IgG3 [Kalfa, 2016]. Intravascular destruction of RBCs through complement mediated mechanisms contributes in only a minor percentage of WAIHA patients. In most patients, erythrocytes coated by warm reacting IgG are bound by spleen macrophages via FcR, which causes them to be either phagocytosed or have part of their membrane removed in the spleen. In the latter case they form microspherocytes that are then subject to further destruction during their next passage through the spleen [Kalfa, 2016]. CD8⁺ T cells, and natural killer (NK cells) may also contribute to RBC lysis through antibody dependent cell mediated cytotoxicity (ADCC). RVT-1401, by reducing the levels of anti-RBC IgG, is hypothesized to be effective for the treatment of patients with WAIHA.

The clinical presentation of WAIHA is characterized by fatigue, exertional dyspnea, pallor, and splenomegaly. Common laboratory findings include: decreased hemoglobin (Hb), reticulocytosis, elevated unconjugated bilirubin and lactate dehydrogenase, serum aspartate aminotransferase disproportionately higher than serum alanine aminotransferase, and decreased haptoglobin [Kalfa, 2016].

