6.8. Safety Management Criteria for Individual Participants

6.8.1. Liver Chemistry Management Criteria

To ensure subject safety and enhance reliability in determining the hepatotoxic potential of an investigational drug, a standardized process for identification, monitoring and evaluation of liver events is to be followed.

The following two categories of abnormalities / adverse events are to be considered during the course of the study (irrespective of whether classified/reported as an AE or SAE):

1. Liver laboratory triggers. These require repeated assessments of the abnormal laboratory parameter
2. Liver events. These require close observation and follow-up monitoring. Contributing factors are to be recorded on the appropriate CRF(s).

Please refer to Appendix 2 Table 4 for complete definitions of liver laboratory triggers and liver events. Every liver event defined in Appendix 2 Table 5 to be followed up by the investigator or designated personnel at the trial site, as summarized below. Additionally, required actions in case of liver laboratory triggers and liver events are outlined in Appendix 2, Table 5 (Follow up requirements for liver laboratory triggers and liver events). Repeat liver chemistry tests (i.e. ALT, AST, TBL, PT/INR, ALP and G-GT) regularly to confirm elevation and follow trends.

The following additional follow up should also be considered:

- Obtain a more detailed history of symptoms and prior or concurrent diseases.
- Obtain a history of concomitant drug use (including non-prescription medications and herbal and dietary supplement preparations), alcohol use, recreational drug use, and special diets.
- Exclude causes of underlying liver disease, as specified in Section 6.3 Exclusion Criteria
- Perform imaging such as abdominal US, CT or MRI, as appropriate
- Obtain a history of exposure to environmental chemical agents.
- Consider gastroenterology or hepatology consultations.

All follow-up information and procedures performed must be recorded as appropriate in the CRF.

These liver chemistry repeats will be performed using the central laboratory. If results will not be available from the central laboratory, then the repeats can also be performed at a local laboratory to monitor the safety of the subject. If a liver event is subsequently reported, any local liver chemistry tests previously conducted that are associated with this event should have results recorded on the appropriate CRF.

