15.2. Appendix 2: Liver Laboratory Trigger and Liver Event Definitions and Follow-up Requirements

Table 4: Definitions of liver laboratory triggers and liver events

	Definition/ threshold
LIVER LABORATORY TRIGGERS	
 • ALT / AST 3x to ≤ 5x ULN • TBL 1.5x to ≤ 2 x ULN
LIVER EVENTS	
 • ALT or AST > 5 × ULN • ALP > 2 × ULN (in the absence of known bone pathology) • TBL > 2 × ULN (in the absence of known Gilbert syndrome) • ALT or AST > 3 × ULN and INR > 1.5 • Potential Hy’s Law cases (defined as ALT or AST > 3 × ULN and TBL > 2 × ULN [mainly conjugated fraction] without notable increase in ALP to > 2 × ULN) • Any clinical event of jaundice (or equivalent term) • ALT or AST > 3 × ULN accompanied by (general) malaise, fatigue, abdominal pain, nausea, or vomiting, or rash with eosinophilia • Any adverse event potentially indicative of a liver toxicity*

**These events include: hepatic failure, fibrosis, cirrhosis, and other liver damage-related conditions; non-infectious hepatitis; benign, malignant and unspecified liver neoplasms*

TBL: total bilirubin; ULN: upper limit of normal

Table 5: Follow up requirements for liver laboratory triggers and liver events

[figure not shown]
Criterion	Actions required	Follow-up monitoring
Potential Hy’s Law case^a	
 • Discontinue the study treatment immediately • Hospitalize, if clinically appropriate • Establish causality • Record the AE and contributing factors (e.g., conmeds, med hx, lab) in the appropriate CRF 	ALT, AST, TBL, Alb, PT/INR, ALP and GGT until resolution^c (frequency at investigator discretion)
ALT or AST		
> 8 × ULN	
 • Discontinue the study treatment immediately • Hospitalize if clinically appropriate • Establish causality • Record the AE and contributing factors (e.g., conmeds, med hx, lab) in the appropriate CRF 	ALT, AST, TBL, Alb, PT/INR, ALP and GGT until resolution^c (frequency at investigator discretion)
> 3 × ULN and INR > 1.5	
 • Discontinue the study treatment immediately • Hospitalize, if clinically appropriate • Establish causality • Record the AE and contributing factors (e.g., conmeds, med hx, lab) 	ALT, AST, TBL, Alb, PT/INR, ALP and GGT until resolution^c (frequency at investigator discretion)

[figure not shown]
Criterion	Actions required	Follow-up monitoring
	in the appropriate CRF	

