Jaundice	
 Discontinue the study treatment immediately Hospitalize the subject Establish causality Record the AE and contributing factors (e.g., conmeds, med hx, lab) in the appropriate CRF 	ALT, AST, TBL, Alb, PT/INR, ALP and GGT until resolution^c (frequency at investigator discretion)
Any AE potentially indicative of a liver	
 Consider study treatment interruption or discontinuation Hospitalization if clinically 	Investigator discretion

[figure not shown]
Criterion	Actions required	Follow-up monitoring
toxicity*	appropriate 
 • Establish causality • Record the AE and contributing factors (e.g., conmeds, med hx, lab) in the appropriate CRF 	

[figure not shown]
Elevated ALT/AST > 3 × ULN and TBL > 2 × ULN but without notable increase in ALP to > 2 × ULN^b(General) malaise, fatigue, abdominal pain, nausea, or vomiting, or rash with eosinophilia^cResolution is defined as one of the following: (1) return to baseline values, (2) stable values at three subsequent monitoring visits at least 2 weeks apart, (3) remain at elevated level after a maximum of 6 months, (4) liver transplantation, and (5) death.

At the investigator’s discretion, investigation(s) for contributing factors to the liver event may include: serology tests, imaging, pathology assessments, hepatologist consultation; obtaining more detailed history of symptoms and prior or concurrent diseases, history of concomitant drug use, and exclusion of underlying liver disease.

[Redacted]

[Redacted]

[Redacted]

[Redacted]

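### The Hy's Law footnote that triggers an immediate stop in Table 5 omits the conjugated-bilirubin condition set by Table 4, so the two tables can call for different actions on the same result.

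*Protocol*

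**What the plan says.** Protocol Appendix 2 (Section 15.2) has two liver tables. The first is headed "Table 4: Definitions of liver laboratory triggers and liver events" and gives a potential Hy's Law case as "ALT or AST > 3 × ULN and TBL > 2 × ULN [mainly conjugated fraction"], provided ALP has not risen above 2 × ULN.

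The second is headed "Table 5: Follow up requirements for liver laboratory triggers and liver events". For a potential Hy's Law case its first action is "Discontinue the study treatment immediately". The footnote that explains this row reads "Elevated ALT/AST > 3 × ULN and TBL > 2 × ULN but without notable increase in ALP", again with 2 × ULN as the ALP limit. The ALT/AST, total bilirubin and ALP thresholds match Table 4; the conjugated condition is absent.

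Section 6.8.1 points both ways. It says "Please refer to Appendix 2 Table 4 for complete definitions of liver laboratory triggers and liver events", and then "Every liver event defined in Appendix 2 Table 5 to be followed up by the investigator".

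Section 3.2 lists among the common laboratory findings of warm autoimmune hemolytic anemia "elevated unconjugated bilirubin and lactate dehydrogenase, serum aspartate aminotransferase disproportionately higher than serum alanine aminotransferase".

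**The concern.** The conjugated condition helps to separate hepatocellular injury from hemolysis, and hemolysis is the disease under study. Inclusion criterion 6 selects for it by requiring low haptoglobin and raised LDH. The definition without the condition sits beside the stop instruction, where a site with a new result will look. Two sites could therefore act differently on identical values, and a participant could be taken off drug without a retest because of the disease being treated.

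The Hy's Law row also does not ask for a hemolysis test. Table 5 asks for one only in the row for isolated bilirubin above 2 × ULN. Elsewhere the protocol makes allowance for the disease: Section 6.9.1 exempts hemoglobin decrease from the Grade 4 stop, and WAIHA signs and symptoms from the Grade 3 hold.

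**Working it through.** The documents give no figure to reproduce and no event rate. The check applies each definition to the same result and reads off the action.

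**Assumptions.** Mainly conjugated is taken as direct bilirubin above 50% of total; the protocol gives no cut-off. Asymptomatic is taken as none of the symptoms in Table 5 footnote b (malaise, fatigue, abdominal pain, nausea, vomiting, or rash with eosinophilia).

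**Worked case.** AST 3.5 × ULN, total bilirubin 2.5 × ULN with 20% direct, ALP 1 × ULN, INR at most 1.5, no footnote b symptom, no jaundice.

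- Table 5 footnote: 3.5 > 3, 2.5 > 2 and 1 ≤ 2, so the case is met and drug stops at once.
- Table 4: direct = 0.20 × 2.5 = 0.50 and indirect = 2.5 − 0.50 = 2.00, in units of the total-bilirubin ULN. The rise is mainly unconjugated, so this is not a Hy's Law case. Since 3 < 3.5 ≤ 5, the ALT/AST row gives a repeat within a week, then close observation if confirmed.

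**Varying the direct fraction** at total bilirubin 2.5 × ULN, other values as above:

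| Direct fraction | Direct (× total ULN) | Table 5 footnote | Table 4 Hy's Law case? |
|---|---|---|---|
| 10% | 0.25 | stop | no |
| 20% | 0.50 | stop | no |
| 30% | 0.75 | stop | no |
| 50% | 1.25 | stop | no |
| 60% | 1.50 | stop | yes, stop |

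**Varying AST** with a direct fraction of 10% to 50%. The bilirubin row is headed as isolated, so it is unclear whether it applies when AST is also raised. Both readings are shown.

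| AST (× ULN) | Table 5 footnote | Table 4, ALT/AST row only | Table 4, bilirubin row also applied |
|---|---|---|---|
| 3.5, 5.0 | stop | repeat within a week | repeat within 48 hours, stop if it persists |
| 6.0, 8.0 | stop | repeat within 48 hours, stop if it persists beyond 2 weeks | repeat within 48 hours, stop if it persists |
| 9.0 | stop | stop (above 8) | stop |

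The definitions therefore lead to different actions for AST above 3 and up to 8 × ULN with mainly unconjugated bilirubin. On either Table 4 reading a retest comes first; under the footnote none does. With fatigue, jaundice or INR above 1.5, both routes stop immediately.

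**Effect of restoring the phrase alone.** If the bilirubin row is confined to isolated rises, AST 3.5 with unconjugated bilirubin 2.5 gets a repeat within a week. Normal AST with the same bilirubin gets a repeat within 48 hours and a stop if it persists. The more abnormal result would be handled less strictly, so the correction must also name the row that applies.

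**The case against.** The strongest reply is that the documents largely settle the matter. Table 4 is titled as definitions, Table 5 as follow-up, and Section 6.8.1 sends the reader to Table 4 for the complete definitions. Its later mention of events defined in Table 5 occurs in a sentence about follow-up and may be a loose cross-reference. This carries weight: Table 4 is the better-supported reading. It does not remove the problem, because the stop instruction and the shorter definition sit together.

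The second reply is that the divergent group is small. Inclusion criterion 7 requires documented anemia symptoms and names fatigue as an example; fatigue with AST above 3 × ULN stops drug under either definition. This also stands, though not every participant need be fatigued: weakness, dizziness, shortness of breath and chest pain are among the other examples, and none is in footnote b.

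The third reply is that the footnote errs towards stopping. That is correct. The cost is an unnecessary or inconsistent stop, not missed liver injury.

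A reader might infer that the footnote will commonly take participants off drug for hemolysis, or that correcting it would prevent such stops. The documents support neither. Section 3.2 does not say that AST exceeds 3 × ULN, and no frequency is given. Persistent isolated bilirubin above 2 × ULN (outside known Gilbert syndrome), jaundice, and AST above 3 × ULN with fatigue all still stop drug, and hemolysis can contribute to each.

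A reader might also want an upper AST/ALT limit in exclusion criterion 9, which admits values of 1.5 × ULN or more on clear imaging. That is a separate design preference. Exclusions 10 and 16 already leave the decision to the investigator, and the footnote discrepancy gives no ground for a cap.

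**Conclusion.** The discrepancy is real and minor. One condition in a stopping-rule definition appears in Table 4 and is missing from the Table 5 footnote, and it bears on a common laboratory feature of the disease. The footnote is one continuous sentence where the phrase would stand, so lost or redacted text is an unlikely explanation.

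The size is an immediate stop against a retest first. It is confined to AST or ALT above 3 and up to 8 × ULN with mainly unconjugated bilirubin above 2 × ULN, ALP at most 2 × ULN, INR at most 1.5, no footnote b symptom and no jaundice. The exact boundary by direct fraction rests on the assumed 50% cut-off.

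The SAP Introduction reports the study paused with 5 participants enrolled in Cohort 1 and a listings-only report. It would be wrong to infer that reported results are affected; nothing in the documents shows that any participant met this pattern. The correction matters for further enrolment or reuse of the appendix.

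**What to change.** 1. In the Table 5 Hy's Law footnote, add the mainly-conjugated condition after the bilirubin threshold, or replace the footnote with a reference to the Table 4 definition.
2. State in Table 5 that AST or ALT above 3 × ULN with mainly unconjugated bilirubin above 2 × ULN follows at least the row for bilirubin above 2 × ULN: repeat within 48 hours, stop if it persists, and test for hemolysis. The combined pattern is then handled no less strictly than isolated bilirubin.

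The cost is two short text changes. Section 8.3.4 already includes total and direct bilirubin, so no new test is needed. The downside is that liver injury masked by concurrent hemolysis would be retested before drug is stopped. The stops for AST or ALT above 8 × ULN, INR above 1.5, footnote b symptoms and jaundice are unchanged. The gain is consistent conduct and a retest before stopping; a persistent rise would still end treatment.

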**ABBREVIATIONS**

ADA	Anti-drug antibody
ADCC	Antibody dependent cell mediated cytotoxicity
AE	Adverse event
AESI	Adverse event of special interest
AIHA	Autoimmune hemolytic anemia
ALT	Alanine aminotransferase
AST	Aspartate aminotransferase
ATC	Anatomical Therapeutic Chemical
ATP	Adult treatment panel
BMI	Body mass index
BUN	Blood urea nitrogen
CI	Confidence intervals
CLL	Chronic lymphocytic leukemia
CO 2	Carbon dioxide
CPK	Serum creatine phosphokinase
CTCAE	Common Terminology Criteria for Adverse Events

ECG	Electrocardiogram
FSH	Follicle stimulating hormone
GCP	Good Clinical Practice
GGT	Gamma glutamyl transferase
Hb	Hemoglobin
HBV	Hepatitis B virus
HCV	Hepatitis C virus
HIV	Human immunodeficiency virus
IB	Investigator's brochure
ICF	Informed consent form
ICH	International conference on harmonization
IEC	Independent ethics committee
IgA	Immunoglobulin A
IgG	Immunoglobulin G
IgM	Immunoglobulin M
IND	Investigational new drug
INR	International normalized ratio

[figure not shown]
Dated 10 December 2021

IP	Investigational product
IRB	Institutional review board
ITP	Idiopathic thrombocytopenia purpura
ITT	Intent to treat
IUD	Intrauterine device
LDH	Lactic acid dehydrogenase
MCH	Mean corpuscular hemoglobin
MCHC	Mean corpuscular hemoglobin concentration
MCV	Mean corpuscular volume
MedDRA	Medical Dictionary for Drug Regulatory Activities
MRC	Medical Research Council
PD	Pharmacodynamics
PK	Pharmacokinetics
RBC	Red blood cell
SAP	Statistical analysis plan
SGOT	Serum glutamic-oxaloacetic transaminase
SGPT	Serum glutamic-pyruvic transaminase
TBL	Total bilirubin
TEAE	Treatment-emergent adverse event
WAIHA	Warm Autoimmune Hemolytic Anemia
WBC	White blood cell
WHO	World Health Organization

Dated 10 December 2021

## 1 INTRODUCTION

This statistical analysis plan (SAP) contains the analysis information for the definition of the analysis populations, derivation of variables, convention of analysis scope, and statistical methodology for the analyses of safety and efficacy of RVT-1401 in the treatment of subjects with Warm Autoimmune Hemolytic Anemia (WAIHA). Based upon a composite review and data suggesting a drug-related effect of RVT-1401 on lipids, the study was paused, and a final analysis of Cohort 1 is being conducted based on the analyses outlined in this SAP. Subjects whose treatment was paused are referred to as curtailed.

At the time of the pause, 5 subjects had been enrolled in Cohort 1; 2 subjects completed the study through the Week 20 visit, 1 subject Early Terminated after Week 3, and 2 subjects were in the treatment period at the time of the pause. The analyses outlined in this plan pertain to the analysis of available data for Cohort 1.

The SAP Version 2.0 was created during the writing of the interim CSR for Cohort 1. A Sponsor decision was made to only include listings in the CSR given the small number of subjects, and SAP Version 2.0 reflects this decision.

This version of the SAP (Version 3.0) made further changes (such as removing all derived variables) to the SAP Version 2.0 to better align with the decision made to only include listings in the CSR.

## 2 OBJECTIVES AND ENDPOINTS

### 2.1 Objectives

The objective of the study is to investigate the safety, tolerability, pharmacokinetics (PK), pharmacodynamics (PD), and efficacy of RVT-1401 (680 mg/weekly and 340 mg/weekly) in subjects with WAIHA.

### 2.2 Endpoints

#### 2.2.1 Primary Endpoints

The primary endpoints are as follows:

- The proportion of responders at Week 13 (defined as Hb level  $\geq 10$ g/dL with at least a  $\geq 2$  g/dL increase from baseline without rescue therapy or blood transfusions in the previous two weeks).
- Assessment of safety and tolerability by analysis of adverse event (AE) data and changes from baseline in vital signs, ECGs, and clinical laboratory values.

[figure not shown]
[figure not shown]
[figure not shown]
[figure not shown]
[figure not shown]
[figure not shown]
#### 2.2.2 Secondary Endpoints

- Change from baseline in Hb levels,
- Time to response,
- Change from baseline in hematocrit levels,

Dated 10 December 2021

- Proportion of subjects with Hb levels in the normal range at Week 13,
- Time to achieving Hb levels in the normal range,
- Change from baseline in FACIT-F score,
- Change from baseline in Medical Research Council (MRC) breathlessness scale,
- Change from baseline in EQ-5D-3L score,
- Change from baseline in levels of total IgG & IgG subclasses (1-4),
- Concentration of RVT-1401 at pre-dose,
- Change from baseline in LDH, bilirubin, and haptoglobin, and
- Immunogenicity determined by change from pre-dose in anti-RVT-1401 antibodies, and characterization of any anti-RVT-1401 antibodies to confirm neutralization potential.

### 2.2.3 Exploratory Endpoints

- 
- 
- 
- 
- 
- 

## 3 STUDY DESIGN

This is a Phase 2, non-randomized, sequential, open-label study to investigate the safety, tolerability, PK, PD, and efficacy of RVT-1401 (680 mg/weekly and 340 mg/weekly) in subjects with WAIHA. Two cohorts of subjects will be enrolled in a non-randomized sequential approach. Subjects will be enrolled into Cohort 1 (680 mg/weekly) first followed by Cohort 2 (340 mg/weekly). (See 5.2 Study Diagram and Flow Chart)

[figure not shown]
Following the initial dose at the Baseline Visit (Week 1, Day 1), study visits will occur weekly throughout the treatment period. Following the final dose at Week 12, visits will occur weekly through Week 14 and then at Week 16 and Week 20. Safety, PK, PD, and clinical assessments will be collected throughout the study.

### 3.1 Sample Size and Statistical Power Consideration

The sample size for this study was not determined using statistical methods. The sample size was chosen based on clinical and recruitment considerations for this Phase 2 study.

Dated 10 December 2021

### 3.2 Study Diagram and Flow Chart

\*\*Note-Cohort 1 will enroll first followed by Cohort 2

### 3.3 Time and events table

Study Timepoint (Weeks)	Screening  Within 30 days	Treatment Period (Weeks)												Follow-up Period (Weeks)				Early Withdrawal Visit
		1 (B/ L)	2	3	4	5	6	7	8	9	10	11	12	13	14	16	20	
Time Window (days)			+/-1 day	+/-2 days	+/-2 days	+/-2 days	+/- 2 days											
Informed consent	X																	
Inclusion/exclusion criteria	X	X																
Demographics and medical history 	X																	
Height	X																	
Body weight	X	X																
Complete physical examination	X	X																
Brief physical examination																	X	X
Vital signs 	X	X	X	X	X	X	X	X	X	X	X	X	X	X	X	X	X	X
12-lead Electrocardiogram 	X	X		X					X				X				X	X
Pregnancy test  (females)	X	X	X	X			X		X		X		X	X			X	X
Viral Serology	X																	
Vaccine Titers 		X												X			X	X
QuantiFERON® – TB GOLD	X																	
Urinalysis 	X	X		X		X		X		X		X		X		X	X	X
Blood chemistry and hematology 	X	X	X	X	X	X		X		X		X		X	X	X	X	X
Fasting Lipid Panel 		X												X			X	X

Dated 10 December 2021

	Screening 	Treatment Period (Weeks)												Follow-up Period (Weeks)				Early Withdrawal Visit
Study Timepoint (Weeks)	Within 30 days	1 (B/ L)	2	3	4	5	6	7	8	9	10	11	12	13	14	16	20	
Time Window (days)			+/-1 day	+/-2 days	+/-2 days	+/-2 days	+/- 2 days											
Serum complement (CH50, C3) 		X		X		X		X		X		X		X		X	X	X
Immunoglobulins (IgM, IgA) 		X		X		X		X		X		X		X		X	X	X

Dated 10 December 2021

Study Timepoint (Weeks)	Screening 	Treatment Period (Weeks)												Follow-up Period (Weeks)				Early Withdrawal Visit
	Within 30 days	1 (B/L)	2	3	4	5	6	7	8	9	10	11	12	13	14	16	20	
Time Window (days)			+/-1 day	+/-2 days	+/-2 days	+/-2 days	+/-2 days											
RVT-1401 PK sampling 		X	X	X	X	X	X		X		X		X	X				X
Total IgG 	X	X	X	X	X	X	X		X		X		X	X	X	X	X	X
Immunoglobins (IgG subclasses) 		X		X			X		X		X			X		X	X	X
Anti- RVT-1401 antibody 		X		X		X			X					X			X	X
NAb Assessment 		X		X		X			X					X			X	X
Drug administration		X	X	X	X	X	X	X	X	X	X	X	X	X				
Injection Site Reaction 		X	X	X	X	X	X	X	X	X	X	X	X					
FACIT-F Scale 		X		X		X		X		X		X		X		X	X	X
MRC Breathlessness Scale 		X		X		X		X		X		X		X		X	X	X
EQ-5D-3L 		X				X				X				X		X	X	X
Satisfaction Questionnaire														X				X
Adverse events	X	X	X	X	X	X	X	X	X	X	X	X	X	X	X	X	X	X
Concomitant medication	X	X	X	X	X	X	X	X	X	X	X	X	X	X	X	X	X	X

1. Screening can take place over multiple days.  
 2. Assessments collected on dosing days will be collected pre-dose.

Dated 10 December 2021

3. Pregnancy tests will be collected pre-dose (via urine dipstick) on dosing days where specified. Serum pregnancy tests should be collected at screening and the final follow up visit.
4. Microalbumin/creatinine ratio at baseline, Week 13, and Week 20 only.
5. Subjects with treatment emergent positive results (change from baseline) for anti- RVT-1401 antibody at Week 20 will be requested to return at approximately 6-, 9-, and 12-months post-dose for additional samples or until their result is no longer positive. However, for purposes of safety follow-up and database lock participation ends at the Week 20 visit.
6. Two samples for IgG will be collected: one will be sent to the central lab for safety monitoring, while the other sample will be sent to Intertek as the PD endpoint.
7. Local injection site reactions will be assessed at approximately 10 minutes post dose.
8. Hematology, HbA1c and [REDACTED] will be drawn for site local laboratory analysis, at minimum, and results collected in the instance where central laboratory samples are received hemolyzed. If other central laboratory tests are received hemolyzed, the local result will be captured in the eCRF.
9. History of WAIHA and prior WAIHA treatments will be captured in the eCRFs.

